3.6.3.2 Analysis of suicidality assessment

The number (%) of participants with suicidal ideation, suicidal behavior, and self-injurious behavior without suicidal intent based on the C-SSRS during treatment will be summarized. A shift table for baseline versus during treatment responses in Part A and Part A + Part B will be provided according to the categories of no suicidal ideation or behavior, suicidal ideation and suicidal behavior.

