### **Medical conditions**

E 01. Participants with a history of seizure or epilepsy (History of febrile seizure during childhood is allowed).

E 02. Participants with central IV lines, such as a peripherally inserted central catheter (PICC) or midline or port-a-cath lines.

E 03. Participants with a significant cognitive impairment, psychiatric disease, other neurodegenerative disorder (eg, Parkinson disease or AD), substance abuse, other causes of neuromuscular weakness, or any other condition that would make the participants unsuitable for participating in the study or could interfere with assessment or completing the study in the opinion of the Investigator.

E 04. Participants with a history of recent serious infection (eg, pneumonia, septicemia) within 4 weeks of the screening visit; infection requiring hospitalization or treatment with IV antibiotics, antivirals, or antifungals within 4 weeks of screening; or chronic bacterial infection (such as tuberculosis) deemed unacceptable as per the Investigator's judgment.

E 05. Participants with an active herpes zoster infection within 2 months prior to the screening visit.

E 06. Participants with a documented history of attempted suicide within 6 months prior to the screening visit, present with suicidal ideation of category 4 or 5 on the Columbia Suicide Severity Rating Scale (C-SSRS), or in the Investigator's judgment are at risk for a suicide attempt.

E 07. Participants with a history of unstable or severe cardiac, pulmonary, oncological, hepatic, or renal disease or another medically significant illness other than ALS precluding their safe participation in this study.

E 08. Participants who are pregnant or are currently breastfeeding.

E 09. Participants with a known history of allergy to any ingredients of SAR443820 (mannitol, lactose monohydrate, sodium starch glycolate, colloidal silicon dioxide, magnesium stearate, hypromellose, titanium dioxide, polyethylene glycol, and microcrystalline cellulose).

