## 7 DISCONTINUATION OF STUDY INTERVENTION AND PARTICIPANT DISCONTINUATION/WITHDRAWAL

### 7.1 DISCONTINUATION OF STUDY INTERVENTION

#### 7.1.1 Permanent discontinuation

The study intervention should be continued whenever possible.

In rare instances, it may be necessary for a participant to permanently discontinue the study intervention.

In case of the following events, permanent discontinuation of the IMP is mandatory. This list is not intended to be exclusive.

- The Investigator or Sponsor determines it is in the best interest of the participant
- Occurrence of AEs or any other medical condition that, in the opinion of the Investigator or Sponsor, may jeopardize the participant's safety or data integrity. These include, but are not limited to, abnormal livers tests and meeting the stopping criteria (see Appendix 6 [\[Section 10.6\]](#))
- Noncompliance with the protocol, including the dosing regimen and visits
- Pregnancy of a female participant
- Any IMP discontinuation lasting longer than 2 weeks accumulative in Part A or 8 weeks accumulative in Part B
- Occurrence of convulsions
- Initiation of riluzole and/or edaravone and/or the combination of sodium phenylbutyrate and taurursodiol treatment during Part A

Any abnormal laboratory value or ECG parameter will be immediately rechecked for confirmation after 24 hours before making a decision regarding permanent discontinuation of the IMP for the concerned participant.

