#### **8.2.7 Suicidal ideation and behavior (SIB) risk monitoring**

SAR443820 crosses the blood-brain barrier. Assessment of suicidal ideation and behavior/treatment-emergent suicidal ideation and behavior will be monitored during ACT16970

using the C-SSRS. For safety reasons, the C-SSRS will be administered throughout the study by the Investigator or delegated to an individual who is certified to administer the scale.

Study intervention administration must be interrupted if a participant scores “yes” on items 4 or 5 of the Suicidal Ideation Section of the C-SSRS or “yes” on any item of the Suicidal Behavior Section. A mental health professional will be consulted and will decide whether the study intervention can be restarted and if any additional risk mitigation strategies are required (eg, increased monitoring, antidepressant administration).

Participants being treated with the study intervention should be monitored appropriately and observed closely for suicidal ideation and behavior or any other unusual changes in behavior. Especially at the beginning and end of the course of treatment, consideration should be given to discontinuing the study medication in participants who experience signs of suicidal ideation or behavior following a risk assessment.

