### Events meeting the AE definition

- Any abnormal laboratory test results (hematology, clinical chemistry, or urinalysis) or other safety assessments (eg, ECG, radiological scans, and vital signs measurements), including those that worsen from baseline, considered clinically significant in the medical and scientific judgment of the Investigator (ie, not related to progression of underlying disease), eg:
  - Symptomatic, and/or
  - Requiring either corrective treatment or consultation, and/or
  - Leading to IMP discontinuation or modification of dosing, and/or
  - Fulfilling a seriousness criterion, and/or
  - Defined as an AESI.
- Exacerbation of a chronic or intermittent pre-existing condition including either an increase in frequency and/or intensity of the condition.
- New conditions detected or diagnosed after study intervention administration even though it may have been present before the start of the study.
- Signs, symptoms, or the clinical sequelae of a suspected drug-drug interaction.
- Signs, symptoms, or the clinical sequelae of a suspected overdose of either study intervention or a concomitant medication.
- "Lack of efficacy" or "failure of expected pharmacological action" per se will not be reported as an AE or SAE. Such instances will be captured in the efficacy assessments. However, the signs, symptoms, and/or clinical sequelae resulting from lack of efficacy will be reported as AE or SAE if they fulfill the definition of an AE or SAE.
- The signs, symptoms, and/or clinical sequelae resulting from lack of efficacy will be reported as AE or SAE if they fulfill the definition of an AE or SAE.

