**E) Is a congenital anomaly/birth defect**

**F) Is a suspected transmission of any infectious agent via an authorized medicinal product**

**G) Other situations:**

- Medical or scientific judgment should be exercised by the Investigator in deciding whether SAE reporting is appropriate in other situations such as significant medical events that may jeopardize the participant or may require medical or surgical intervention to prevent 1 of the other outcomes listed in the above definition. These events should usually be considered serious.
  - Note: The following list of medically important events is intended to serve as a guideline for determining which condition has to be considered as a medically important event. The list is not intended to be exhaustive:
- Intensive treatment in an emergency room or at home for:
  - Allergic bronchospasm
  - Blood dyscrasias (ie, agranulocytosis, aplastic anemia, bone marrow aplasia, myelodysplasia, pancytopenia, etc)
  - Convulsions

- Development of drug dependence or drug abuse
- ALT  $>3 \times$  ULN + total bilirubin  $>2 \times$  ULN or asymptomatic ALT increase  $>10 \times$  ULN
- Suicide attempt or any event suggestive of suicidality
- Syncope, loss of consciousness (except if documented as a consequence of blood sampling)
- Bullous cutaneous eruptions

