- Any treatment-emergent AESI
- Any TEAE considered by the investigator as related to IMP

An additional overview summary including the number and rate of events will be provided.

The AE summaries of [Table 5](#) will be generated with number (%) of participants experiencing at least one event.

Listings of SAEs from randomized participants, AEs from participants who are treated but not randomized, AEs leading to treatment/study discontinuation and severe AEs will be provided.

Table 5 - Analyses of adverse events

Type of AE	MedDRA levels
All TEAEs	Primary SOC and PT
Common TEAE ($\geq 2\%$ in any group)	PT
TEAEs related to IMP as per Investigator's judgment	Primary SOC and PT
TEAE by maximal intensity	PT
Treatment emergent SAEs	Primary SOC and PT
Treatment emergent SAEs related to IMP as per Investigator's judgment	Primary SOC and PT
Treatment emergent AESIs	AESI category and PT
TEAEs leading to permanent intervention discontinuation	Primary SOC and PT
TEAEs leading to death ^b	Primary SOC and PT
Pretreatment AEs	Overview ^a
Post-treatment AEs	Primary SOC and PT
	Overview ^a
	Primary SOC and PT

^a Will include the following AE categories: any AEs, any serious AEs, any AEs leading to death, any AEs leading to permanent intervention discontinuation

^b Death as an outcome of the AE as reported by the Investigator in the AE page

Analysis of deaths in Part A and Part A + Part B

In addition to the analyses of deaths included in [Table 5](#), the number (%) of participants in the following categories will be provided:

- Deaths during the treatment-emergent period and post-treatment period
- Deaths in non-randomized participants or randomized but not treated participants

Analysis of adverse events of special interest (AESIs) in Part A and Part A + Part B

Adverse events of special interest (AESIs) will be selected for analyses as indicated in [Table 6](#). Number (%) of participants experiencing at least one event will be provided for each event of interest. Tables will be sorted as indicated in [Table 4](#). A listing of AESIs will also be provided.

Table 6 - Selections for AESIs

AESIs	Selection
Pregnancy of a female participant or female partner of a male participant	Dedicated CRF page (AECAT="PREGNANCY DATA")
Symptomatic overdose (serious or non-serious) with IMP	Dedicated CRF page (AECAT="OVERDOSE DATA"; must be symptomatic and AESI marked "Y")
Convulsions	CMQsn00079 for selection and AESI marked "Y"

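### The C-SSRS shift table pools all suicidal ideation levels, so worsening across the protocol's drug-interruption threshold is tabulated as no change

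*SAP*

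**What the plan says.** SAP 3.6.3.2 plans two C-SSRS outputs, both descriptive. The first is a count: n (%) of participants with "suicidal ideation, suicidal behavior, and self-injurious behavior without suicidal intent based on the C-SSRS during treatment will be summarized". The second is a shift table of baseline against on-treatment response, for Part A and for Part A + Part B, built "according to the categories of no suicidal ideation or behavior, suicidal ideation and suicidal behavior". The section divides ideation no further.

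The protocol does divide it. Section 8.2.7 makes interruption of study drug mandatory when a participant scores yes "on items 4 or 5 of the Suicidal Ideation Section of the C-SSRS or" on any item of the behavior section. A mental health professional then decides whether dosing may restart. Exclusion criterion E 06 uses the same cut at entry and bars those who "present with suicidal ideation of category 4 or 5 on the Columbia Suicide Severity Rating Scale".

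SAP 3.1 sets the C-SSRS baseline as the worse of two assessments: the six-month lookback at screening and the since-last-visit form on Day 1.

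**The concern.** A shift table is meant to show who got worse on treatment. This one has no boundary at the only ideation level on which the protocol acts. Because E 06 turns away category 4-5 but not lower ideation, most baseline ideation should sit at 1-3. That is the starting point from which worsening to 4-5 goes unseen. A participant who starts with none and reaches 4 or 5 does show as worse, but in the same cell as someone who reaches 1.

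The study report could therefore present a C-SSRS shift table that gives no comparison between arms of how many participants newly reached the level at which dosing had to stop. Protocol 8.2.7 introduces this monitoring by noting that the drug crosses the blood-brain barrier, so a reader of the safety section can be expected to look for that comparison.

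**Working it through.** The plan states no figure on this point, so there is none to reproduce. The check is a comparison of texts and a count of cells.

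**Inputs**
- Shift categories: three, with ideation as one (SAP 3.6.3.2).
- Interruption trigger: ideation item 4 or 5, or any behavior item (Protocol 8.2.7).
- Entry restriction: category 4-5 excluded, lower levels not (Protocol 5.2, E 06).
- Assumption: ideation is scored on five ordered levels, as the numbering of items 4 and 5 implies. The documents do not print the scale. The conclusion needs only that levels below 4 exist.

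**Count of upward moves without behavior**

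Among five ideation levels there are 5 × 4 / 2 = 10 upward moves. Those that start at 1, 2 or 3 and end at 4 or 5 number 3 × 2 = 6. The other four are 1 to 2, 1 to 3, 2 to 3 and 4 to 5. From no ideation there are five further moves, of which two (to 4 or 5) meet the trigger.

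| Move on treatment | Moves | Planned table | Split at 4-5 |
|---|---|---|---|
| Upward within 1-3 | 3 | No change | No change |
| 1-3 to 4-5 | 6 | No change | Worse |
| 4 to 5 | 1 | No change | No change |
| None to 1-3 | 3 | None to ideation | None to 1-3 |
| None to 4-5 | 2 | None to ideation (same cell) | None to 4-5 |

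All six moves across the threshold from existing ideation lie on the diagonal of the planned table. The two new-onset moves to 4-5 share a cell with the three to 1-3.

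**Do other planned outputs show it?**
- *The n (%) summary in SAP 3.6.3.2.* It names ideation as one item. It neither promises a split by level nor rules one out.
- *Adverse event tables.* Protocol 10.3.1 counts a clinically significant safety finding as an AE when, for example, it is one "Leading to IMP discontinuation or modification of dosing". Such an event could enter the TEAE tables.
- *Serious adverse events.* Protocol 10.3.2 lists "Suicide attempt or any event suggestive of suicidality" among its examples of medically important events. SAP 3.6.2 plans a table of treatment-emergent SAEs by SOC and PT, and a listing of SAEs in randomized participants. A case reported as serious would be in both.
- *Discontinuation.* Protocol 7.1.1 makes discontinuation permanent for "Any IMP discontinuation lasting longer than 2 weeks accumulative in Part A or 8 weeks accumulative in Part B", and SAP Table 5 has a row for "TEAEs leading to permanent intervention discontinuation". An interruption that ends in restart within those limits is not in that row. SAP 3.6.1 measures exposure without regard to unplanned gaps, so the interruption does not show there either.
- *AESIs.* Suicidality is not on the list in Protocol 8.3.8 or SAP Table 6.

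The AE and SAE routes depend on what the investigator judges and reports, and none of them has to carry the C-SSRS level.

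**The case against.** The strongest reply is that this is table layout. The safety analysis is descriptive with no testing planned. Suicidality is not among the risks in Protocol 2.3.1 and is not an AESI. Protocol 9.4.6 asks for no C-SSRS analysis, so the SAP already gives more than it must. No rule says that a monitoring threshold has to be a shift-table boundary. With very few cases, an SAE listing would tell a reader more than a cell in a sparse table. New cases are also limited: Part B dosing has been paused since 5 December 2023, and C-SSRS is not among the assessments kept after early IMP discontinuation (Protocol 1.3, footnote b in Part A and e in Part B).

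Much of this stands, and it keeps the point small. It does not remove it. The three categories are a stated rule, not a detail left open, and that rule places a protocol-defined stopping event in the no-change cell. The listing helps only where the case was reported as an SAE. Elsewhere the SAP does grade a safety signal by severity: SAP 3.6.3.1 summarizes ALT elevations above 3, 5, 10 and 20 times ULN.

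Three stronger readings are tempting, and the documents do not support them.
- *Participants at ideation 4-5 would be missed or left on drug.* The interruption rule is applied to each participant at the site and does not use this table.
- *Such cases could appear nowhere in the report.* The AE and SAE outputs may show them, and the n (%) summary could be split by level under its present wording.
- *Baseline ideation can never be 4-5 because of E 06.* E 06 turns on how a participant presents and gives no lookback for ideation, whereas the SAP baseline includes a six-month lookback. A 4-5 baseline cannot be excluded.

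**Conclusion.** The point holds as a minor one about a descriptive safety table. As specified, the table shows worsening from ideation 1-3 to 4-5 without behavior as no change and merges new-onset 4-5 with new-onset 1-3. No other output to which the SAP commits gives C-SSRS results by ideation level.

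The number of participants affected is unknown and may be zero, because the documents give no ideation rates at baseline or on treatment. The subset hidden on the diagonal is narrow: baseline ideation at 1-3, on-treatment ideation at 4-5, and no behavior. No efficacy, alpha or power conclusion changes. The finding about the table rests on the SAP text alone. How much it matters in practice depends on counts that the documents do not contain.

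**What to change.** In SAP 3.6.3.2:

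1. Use four shift categories: none; ideation 1-3; ideation 4-5; behavior.
2. Add one n (%) row by arm for participants who meet the Protocol 8.2.7 trigger on treatment (ideation item 4 or 5, or any behavior item), regardless of baseline.

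The row should not be restricted to categories worse than baseline. A participant whose six-month lookback put the baseline at 4-5, and who scores 4 or 5 again on treatment, has dosing interrupted but would drop out of a worse-than-baseline count. With the row left unrestricted, the shift table shows which of those participants are worse than baseline. The row also does not depend on the separate baseline that SAP 3.6 sets for the placebo-to-SAR443820 group in the Part A + Part B summaries.

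The cost is one SAP edit, a 4 × 4 table in place of a 3 × 3 (16 cells instead of 9, some of them sparse) and one extra row. No new data are needed, since the ideation items must already be scored to apply the interruption rule.

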3.7 OTHER ANALYSES

3.7.1 Other variables and/or parameters

3.7.1.1 Pharmacokinetic (PK) analyses

Plasma concentration of SAR443820 will be summarized in the PK population using arithmetic and geometric means, standard deviation, standard error of the mean, coefficient of variation, minimum, median and maximum per sampling time. For drug-treated participants, where concentration values are below the lower limit of quantification (LLOQ), one-half of the LLOQ will be used. Values will be expressed in the tables with no more than three decimal places. These analyses will be performed for all participants received SAR443820 and by baseline body weight (by quartiles).

The population PK analyses will be presented separately from the main clinical study report.

3.7.1.2 Pharmacodynamic (PD) analyses

PD parameters include NfL, chitinase-3-like protein-1, a selected panel of cytokines and chemokines in serum, soluble triggering receptor expressed on myeloid cells-2 in plasma and extracellular domain of p75 in urine. NfL data will be analyzed under secondary endpoints as described in [Section 3.3.1.2](#). The rest of PD parameters will be summarized in Part A by actual treatment group in the safety population using the following descriptive statistics: mean, geometric mean, median, standard deviation, coefficient of variation, minimum, and maximum.

The corresponding change from baseline values will also be provided. Plots of mean (\pm SD) and/or mean change (\pm SD) over time will also be provided for better visualization.

3.7.1.3 PK/PD analysis

Exploratory exposure response analysis will be provided in a standalone report. The documentation of the methods of analysis will be described in a standalone plan.

3.8 INTERIM ANALYSES

A nonbinding interim analysis (IA) for futility may be conducted when approximately 40% of the participants complete Part A, the double-blind placebo-controlled period, or discontinue the study before Week 24. If both stopping criteria for change from baseline in the ALSFRS-R total score to Week 24 and change from baseline in NfL to Week 24 are met, the futility may be declared. An independent statistical group, external to the Sponsor (not involved with the conduct of the study), will conduct this IA and support the DMC activities. At the time of the IA, if the DMC recommends the study to continue, the Sponsor will be informed of the decision without receiving any unblinded results. Only if the DMC considers recommending the study to stop for futility, a prespecified limited number of the Sponsor's senior management team will be informed of the unblinded results. This limited Sponsor's senior management team will decide to stop or continue the study. No one involved in the conduct of the study will have access to the unblinded data. Interim analysis details will be provided in the DMC SAP.

When all participants complete Part A, which is the 24 weeks of double-blind treatment period, or discontinue from the study before Week 24 (ie, last participant last visit for Part A), the final confirmatory analyses for Part A will be performed from the database lock for Part A, and the results will be provided in a study report.

For Part (open label, long-term extension period), interim analyses/reports may be prepared to support regulatory submission or other purpose.

When all participants complete Part B or discontinue from the study before the end of Part B (ie, last participant last visit for Part B), the final analyses for the entire study period will be conducted and the final clinical study report will be generated.

3.9 CHANGES TO PROTOCOL-PLANNED ANALYSES

This section summarizes major statistical changes in the protocol amendment(s).

Major statistical changes in protocol amendment(s)

Amendment Number	Approval Date	Changes	Rationale
2	02-Dec-2022	In MMRM model for change from baseline in continuous endpoints, baseline NfL (if different from the baseline value of the endpoint), use of the combination	Clarification of the terms in MMRM model

Amendment Number	Approval Date	Changes	Rationale
		of sodium phenylbutyrate and taurursodiol (yes vs no), baseline NfL-by-visit interaction (if different from the baseline value of the endpoint-by-visit interaction), baseline value of the endpoint-by-visit interaction are also included, while randomization strata-by-visit interaction is removed.	
5	13-Dec-2023	In MMRM for change from baseline in continuous endpoints, disease duration (first symptom onset to screening visit) and disease duration by visit interaction are also included	Clarification of the terms in MMRM model

4 SAMPLE SIZE DETERMINATION

The proposed sample size ($n = 261$) provides an approximately 80% power to detect a 30% reduction in SAR443820 compared with placebo in the change of ALSFRS-R from baseline at Week 24, assuming a change of █ points from baseline in ALSFRS-R in the placebo arm with a standard deviation of █ points, and a 20% drop-out rate. Sample size is estimated via simulation with a 2-sided 5% significance level.

